1. AMENDMENT HISTORY

Amendment No.	Protocol Version No.	Date issued	Author(s) of changes	Details of Changes made
Pre-approval	2	22.01.2021	[name] [name]	
 1. Samples will now be taken 1 month after the first vaccine dose and 1 month after the second vaccine dose
SA01	2		[name] [name]	
These changes were made at the same time as the response to REC above:
 
 1. Addition of a baseline sample and a 6 month post second vaccine dose sample 2. Access to stored clinical samples for patients (to prevent having to take the baseline sample) 3. An increase in the amount of blood taken at each timepoint 4. Analysis and storage of samples at University of Leicester 5. Transfer of samples to the CRICK Institute
SA02	3	19.02.2021	[name]	
 1. Addition of a survey pack for patients and controls
SA03	4	16/08/2021	[name] [name]	
 1. Addition of additional time points for blood sampling, including before and following any subsequent booster doses. 2. Addition of the ability to transfer samples collaborating centres for analyses that cannot be completed in Leicester under the terms of material transfer agreements agreed between UoL and collaborating centres, 3. Extend the study time period for a further 24 months to allow us to collect the additional blood samples above
NSA01	4.1	03/05/2022	[name]	
 1. Reduction of the sample size to 115

Date: 03/05/2022 Version 4.1

2. SYNOPSIS

Study Title	PHENOTYPING SEROCONVERSION FOLLOWING VACCINATION AGAINST COVID-19 IN PATIENTS ON HAEMODIALYSIS
Internal ref. no.	0810
Trial Design	Prospective observational
Trial Participants	End Stage Kidney Disease on Haemodialysis and Healthy volunteers
Planned Sample Size	95 patients with end stage kidney disease on haemodialysis and 20 healthy volunteers
Planned Trial Period	3 years (36 months)
Primary Objective	
 • To phenotype the 1 month seroconversion following the first vaccination dose and the 1 month and 6 month seroconversion following the second vaccination dose against COVID-19 in haemodialysis patients
Secondary Objectives	
 • To compare rates of 1 month seroconversion following the first vaccination dose and the 1 month and 6 month seroconversion following the second vaccination dose against COVID-19 between patients on maintenance haemodialysis and healthy control volunteers • To assess antibody levels 12, 18 and 24 months post second vaccination. • Assess the antibody response before and 1 month after any booster vaccinations

Date: 03/05/2022 Version 4.1

3. ABBREVIATIONS

AE	Adverse event
AR	Adverse reaction
CI	Chief Investigator
CKD	Chronic Kidney Disease
CRO	Contract Research Organisation
EC	Ethics Committee (see REC)
eGFR	Estimated Glomerular Filtration Rate
ESKD	End Stage Kidney Disease
GCP	Good Clinical Practice
GP	General Practitioner
ICF	Informed Consent Form
NHS	National Health Service
NRES	National Research Ethics Service
PI	Principal Investigator
PIL/S	Participant/ Patient Information Leaflet/Sheet
R&D / R&I	NHS Trust Research &Development / Innovation Department
REC	Research Ethics Committee
SAE	Serious Adverse Event
SAR	Serious Adverse Reaction
TMF	Trial Master File

Date: 03/05/2022 Version 4.1

4. BACKGROUND AND RATIONALE

Patients with end stage kidney disease (ESKD) on haemodialysis are more likely to suffer poorer outcomes following infection with severe acute respiratory syndrome coronavirus 2 (SARS-CoV-2) infection (1). This is likely to be because these patients have higher levels of co-morbid diseases and they are relatively immunosuppressed due to the effects of advanced kidney disease. The humoral response against common viral vaccination is known to be blunted in patients with ESKD (2) and there are data to suggest seroconversion following infection with COVID-19 is blunted in patients with kidney disease (3). A successful programme of vaccination will undoubtedly improve outcomes for patients on haemodialysis, but vaccine testing programmes have not included patients with ESKD. Whilst initial press-coverage of the efficacy of vaccines which are available for use is promising, they are untested in patients on haemodialysis who are known to be relatively immunosuppressed as a result of their renal disease and as such the efficacy for this patient group is not known.

This study will phenotype the IgG antibody response to vaccination for COVID-19 in 95 patients on haemodialysis compared to 20 healthy volunteers. Antibody testing will be conducted at 1 month post first vaccination dose and 1 month and 6 months post second vaccination dose. This will give crucial information as to the efficacy of the vaccine and inform possible requirements for re-vaccination.

Date: 03/05/2022 Version 4.1

5. OBJECTIVES

This study will:

1. Phenotype the 1 month IgG antibody response to the first vaccination dose and the 1 month and 6 month response to the second vaccination dose for COVID-19 in patients on haemodialysis
2. Compare the 1 month IgG antibody response to the first vaccination dose and the 1 month and 6 month response to the second vaccination dose for COVID-19 between patients on haemodialysis and healthy volunteers
3. Assess the antibody response immediately before and 1 month after any booster vaccinations
4. Measure antibody levels 12, 18 and 24 months after their second vaccination

Date: 03/05/2022 Version 4.1

Participants recruited to the study will be contacted via telephone to collect relevant details of medical history and demographics and their medical records will be accessed to collect recent blood test results and historic tests results for COVID-19 (both antigen and antibody tests).

Date: 03/05/2022 Version 4.1

7. TRIAL PARTICIPANTS

7.1 Overall Description of Trial Participants

95 prevalent patients on maintenance haemodialysis and 20 healthy volunteers will be recruited following vaccination for COVID-19.

7.2 Inclusion/Exclusion Criteria (ESKD patients on haemodialysis)

Inclusion Criteria

- Age>18 years
- ESKD on maintenance haemodialysis
- Able and willing to give informed consent
- Have completed or due to complete vaccination against COVID-19

Exclusion Criteria

- Acute kidney injury requiring temporary haemodialysis
- Unable to give informed consent
- Pregnancy

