8. STUDY PROCEDURES

Patients on haemodialysis are currently being vaccinated by invitation in secondary care. As part of routine clinical care, patients are being asked when they attend dialysis whether they have been called for vaccination or whether they have been vaccinated. When they have been vaccinated this is routinely recorded by the clinical staff on the University of Leicester renal database (PROTON). The clinical team will identify people who have been vaccinated through this database and members of the study team (who will also be members of the clinical team) will approach the patients to discuss the study and to give them a PIS should they want to take part. These patients will be followed up at their next dialysis session and if they wish to participate will be consented by a member of the research team.

Healthy volunteers will be identified as members of the clinical team who are having the vaccine or those who contact the study team directly in response to posters advertising the study to healthy volunteers. Once healthy volunteers have been identified in these ways they will be given a PIS by a member of the study team and contacted after 48 hours by a member of the study team. If they wish to take part they will then be consented by a member of the study team.

8.1 *Informed Consent*

In both cases, participants will have a minimum of 48 hours to consider the patient information sheet, and the opportunity to question the study team, or other independent parties to decide whether they will participate in the study.

Written informed consent will then be obtained by means of participant dated signature and dated signature of the person who presented and obtained the informed consent. The person who obtained the consent will be suitably qualified and experienced, and have been authorised to do so by the Chief/Principal Investigator as detailed on the Delegation of Authority and Signature log for the study. The original signed form will be retained at the study site within the Trial Master File (TMF) or Investigator Site File (ISF). A copy of the signed informed consent will be given to participants (or emailed to participants at their request) and a copy retained in the participant medical notes. Written informed consent will be taken prior to any assessments.

8.2 *Screening and Eligibility Assessment*

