Potential participants who are patients on haemodialysis will be screened prior to initial telephone contact by a member of the clinical team involved in patient care based on the

Date: 03/05/2022 Version 4.1

inclusion/exclusion criteria against patients. The clinical team will also screen clinic lists and the COVID-19 vaccination log on PROTON (see above) to identify and approach potential participants at routine dialysis sessions.

Potential participants who are healthy volunteers will be NHS workers at the University Hospital of Leicester. It is anticipated that NHS workers will be amongst the first groups of people to receive the vaccine and these people will be made aware of the study through local poster advertisements in the department of renal medicine at the University Hospitals. Those interested in participating will be asked to contact the study team via email and the study team will then make contact to screen for eligibility, send the PIS and invite to take part as required.

8.3 *Assessments*

For patients on haemodialysis, blood sampling for IgG antibody response to COVID-19 vaccination will take place when the patient attends a routine dialysis appointment 1 month post first vaccination dose and 1 month and 6 months post second vaccination dose (3 samples total). A baseline sample will be obtained from routinely stored clinical samples. Blood will be taken during the patients dialysis at the same time as bloods for routine clinical care with no additional procedures needed when blood is taken. Vaccines currently available or soon to be available require 2 doses before immunity is achieved and the blood antibody tests will be taken 1 month after the first immunisation has been administered and 1 month and 6 months after the second. Blood will be taken from the arterial dialysis line at the start of dialysis so no additional venepuncture is required and no additional visits to a clinical environment are required.

Healthy volunteers will be working in a clinical environment within UHL and will have their blood taken by a trained member of the research team (all of whom are working on the clinical service at UHL) at baseline, 1 month post the first vaccination dose and 1 month and 6 months after the second vaccination dose. This will be arranged in the most practical way and will conform to Hospital protocols on the wearing of personal protective equipment in the clinical environment the blood is taken.

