20. STUDY VISIT TABLE

Visit Name	Haemodialysis patients	Healthy volunteers
Baseline	
Extraction of routine clinical and demographic information and previous relevant investigation, including telephone call if required
 
Extraction of baseline sample from stored clinical samples.
	
Extraction of routine clinical and demographic information and previous relevant investigation, including telephone call if required
 
Attend UHL blood room for IgG antibody testing for COVID

1 month post first vaccine dose visit	Blood taken from arterial line at the start of dialysis when patient attends for regular dialysis session	Attend UHL blood room for IgG antibody testing for COVID
1 month post second vaccine dose	Blood taken from arterial line at the start of dialysis when patient attends for regular dialysis session	Attend UHL blood room for IgG antibody testing for COVID
6 months post second vaccine dose	Blood taken from arterial line at the start of dialysis when patient attends for regular dialysis session	Attend UHL blood room for IgG antibody testing for COVID
Immediately before any planned booster vaccine	Blood taken from arterial line at the start of dialysis when patient attends for regular dialysis session	Attend UHL blood room for IgG antibody testing for COVID
1 month after any booster doses of COVID vaccine	Blood taken from arterial line at the start of dialysis when patient attends for regular dialysis session	Attend UHL blood room for IgG antibody testing for COVID
12 months after second vaccination	Blood taken from arterial line at the start of dialysis when patient attends for regular dialysis session	Attend UHL blood room for IgG antibody testing for COVID
18 months after second vaccination	Blood taken from arterial line at the start of dialysis when patient attends for regular dialysis session	Attend UHL blood room for IgG antibody testing for COVID
24 months after second vaccination	Blood taken from arterial line at the start of dialysis when patient attends for regular dialysis session	Attend UHL blood room for IgG antibody testing for COVID

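### People enrolled after dose 2 cannot give the one-month post-first-dose sample, and carry-forward would fill the gap with a baseline that can mean different things in patients and volunteers

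*Protocol*

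**What the plan says.** The primary objective in the protocol synopsis is "To phenotype the 1 month seroconversion following the first vaccination dose and the 1 month and 6 month seroconversion following the second vaccination dose". The same three time points are used for the comparison between patients and volunteers (protocol sections 2, 5 and 11.1).

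Sections 7.2 and 7.3 share one vaccination criterion: "Have completed or due to complete vaccination against COVID-19". Section 8.3 says what completion involves: "Vaccines currently available or soon to be available require 2 doses before immunity is achieved". Section 7.1 states that both groups "will be recruited following vaccination for COVID-19". For patients, section 8 adds: "The clinical team will identify people who have been vaccinated through this database". None of these passages limits which dose has been given or how long ago. Section 8.1 gives at least 48 hours to decide and then says: "Written informed consent will be taken prior to any assessments".

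On sampling, section 8.3 says that "blood antibody tests will be taken 1 month after the first immunisation has been administered and 1 month and 6 months after the second". The visit table in section 20 lists the "1 month post first vaccine dose visit" with no window and no condition relative to dose 2, whereas for boosters it does place a sample ahead of the dose. Stored clinical samples may be used for the patients' baseline only. Volunteers have their baseline drawn by the study team (sections 6.2, 8.3 and 20).

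Protocol section 11.4 and the SAP's missing-data paragraph both carry the last value forward on an assumption of no change. The SAP defines no time points, sampling windows or analysis sets.

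**The concern.** The eligibility rule and the first-dose outcome do not fit together. The plan admits people for whom the first-dose sample date has passed, or falls after dose 2, and does not say how they enter the first-dose analysis. The only rule that applies to them is carry-forward, and the value before the missing sample is baseline.

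That baseline can mean different things in the two groups. In a patient enrolled late it is a stored sample that may predate vaccination, so a vaccine responder may be counted as a non-responder. In a volunteer enrolled late it is drawn after consent, and therefore after vaccination, so it may already show the response to two doses. At stake are the first-dose rate in patients and one of the three between-group comparisons.

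**Working it through.** **What the plan allows us to reproduce.** The only figure is the sample size, and 95 + 20 = 115 adds up. No expected rate, precision or power is given, so there is no calculation to repeat.

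**Who can give the sample.** Count time from dose 1. Dose 2 falls at I (not stated in either document), consent is at C, and the sample is due at one month.

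- Enrolled after dose 2 (C > I), with I of a month or more: the sample date has passed at consent, so no sample is possible.
- Enrolled after dose 2, with I under a month: either the date has passed, or a sample is possible but is taken after two doses.
- Enrolled between doses, with I longer than a month: the sample is valid if consent comes within the first month, and is missed otherwise.
- Enrolled between doses, with I of about a month or less: the sample falls at or after dose 2.

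The first two cases hold whatever I is. The last depends wholly on I.

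**Size, for illustration.** These values are assumptions and none is in the documents:

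- f is the share enrolled after dose 2, taken as equal in both groups.
- p1 is the true post-first-dose rate, 40%, 60% or 80%, equal in both groups.
- p2 is the post-second-dose rate, 90%.
- Seroconversion is scored as antibody-positive.
- Every late patient has a negative stored baseline.
- Every late volunteer's baseline is drawn once dose 2 has taken full effect.

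Formulas:

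- Usable samples: 95(1 − f) and 20(1 − f), rounded.
- Patients' rate after carry-forward: p1(1 − f).
- Volunteers' rate after carry-forward: p1(1 − f) + p2·f.
- Spurious gap: the difference between these, p2·f.
- Wilson 95% half-width among patients with a usable sample: z·√[p1(1 − p1)/n + z²/(4n²)] / (1 + z²/n), with z = 1.96.

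| f | Usable patients / volunteers | Half-width, patients, p1 = 60% | Patients / volunteers, p1 = 40% | p1 = 60% | p1 = 80% | Spurious gap |
|---|---|---|---|---|---|---|
| 0 | 95 / 20 | 9.7 points | 40% / 40% | 60% / 60% | 80% / 80% | 0 |
| 10% | 86 / 18 | 10.1 | 36% / 45% | 54% / 63% | 72% / 81% | 9 points |
| 25% | 71 / 15 | 11.1 | 30% / 52.5% | 45% / 67.5% | 60% / 82.5% | 22.5 |
| 50% | 48 / 10 | 13.4 | 20% / 65% | 30% / 75% | 40% / 85% | 45 |

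Worked row, f = 25% and p1 = 60%: patients 0.75 × 0.60 = 0.45; volunteers 0.45 + 0.25 × 0.90 = 0.675; gap 0.90 × 0.25 = 0.225.

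Restricting the analysis to valid samples costs little precision by comparison: at f = 25% the half-width widens from 9.7 to 11.1 points.

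The gap need not take this direction. If a late patient's stored sample was itself taken after vaccination, or is positive from past infection, carrying it forward raises the patients' rate instead.

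**The case against.** The case for the plan is a fair one. Recruitment ran alongside the roll-out: patients are asked about vaccination at dialysis and followed up at the next session, volunteers are staff having the vaccine, and section 6.1 describes consecutive patients. Lags may therefore have been short and late enrolment rare. Wide eligibility also has a purpose, because late entrants still inform the six-month, booster and 12-, 18- and 24-month outcomes. First-dose response is one of three time points, and section 6.2 ranks none of them above the others. Carry-forward may never have been meant for visits that predate enrolment. Nor will every baseline be negative, since the protocol collects earlier COVID-19 test results.

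Much of this stands as a limit on size. It does not remove the problem. No passage caps the time since either dose, and the missing-data rule is written without exceptions.

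Two stronger readings are tempting. A reader might infer that the first-dose sample is really a two-dose response even in people enrolled on time. That needs a dosing interval of about a month or less, and neither document gives one. Even then, dose 2 might have been given only days before the sample. A reader might also join the lowest and highest figures in the table into one range for the reported rate. They come from two different mechanisms at assumed proportions, so they do not form a range for any single estimate.

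**Conclusion.** The concern holds in limited form. By the protocol's own rules, some eligible participants cannot give a valid first-dose sample, and carry-forward applied as written would replace their result with a baseline that can differ in meaning between the groups. The first-dose rate and its comparison could be biased in either direction.

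The number affected cannot be determined from the documents. The 9 to 45 point gaps above rest entirely on the assumed late share, the assumed p2 and the worst-case baselines, and should be read as illustration only. Contamination by dose 2 among people enrolled on time remains conditional on the unstated interval. The second-dose time points are less exposed, although someone enrolled more than a month after dose 2 also misses the first of them.

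**What to change.** In the SAP:

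1. Define the first-dose outcome only for participants with a sample about one month after dose 1 and before dose 2. State the window, and establish membership from recorded dose and sample dates. The itemised clinical data in section 8.3 name the vaccine make and type but not the dose dates, so both dates should be captured.
2. Do not carry baseline, or any other value, into this time point.
3. Count late enrollees only for outcomes whose sample date falls after their enrolment.
4. Report the denominator by group at each time point, with the number excluded from the first-dose analysis.

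Optionally, where a suitable routinely stored patient sample exists for the missed date, extend the stored-sample permission to it by amendment. Report that result as a sensitivity analysis only, because volunteers have no such route and ascertainment would differ between groups.

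Bringing the sample forward to the last attendance before dose 2 is not advised. It would turn a fixed one-month outcome into one of variable timing. Nothing here concerns when doses are given.

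The cost is SAP wording, retrieval of dose dates and a smaller stated denominator for the first-dose rate. No visits are added, and the analysis steps remain feasible if enrolment has finished.

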7.3 Healthy Controls Inclusion/Exclusion criteria

Inclusion Criteria

- Age>18 years
- Able and willing to give informed consent#
- Have completed or due to complete vaccination against COVID-19

Exclusion Criteria

- History of immunosuppression
- Use of immunosuppressive medications in prior 12 months
- Known history of chronic kidney disease
- Pregnancy

Date: 03/05/2022 Version 4.1

8. STUDY PROCEDURES

Patients on haemodialysis are currently being vaccinated by invitation in secondary care. As part of routine clinical care, patients are being asked when they attend dialysis whether they have been called for vaccination or whether they have been vaccinated. When they have been vaccinated this is routinely recorded by the clinical staff on the University of Leicester renal database (PROTON). The clinical team will identify people who have been vaccinated through this database and members of the study team (who will also be members of the clinical team) will approach the patients to discuss the study and to give them a PIS should they want to take part. These patients will be followed up at their next dialysis session and if they wish to participate will be consented by a member of the research team.

Healthy volunteers will be identified as members of the clinical team who are having the vaccine or those who contact the study team directly in response to posters advertising the study to healthy volunteers. Once healthy volunteers have been identified in these ways they will be given a PIS by a member of the study team and contacted after 48 hours by a member of the study team. If they wish to take part they will then be consented by a member of the study team.

8.1 *Informed Consent*

In both cases, participants will have a minimum of 48 hours to consider the patient information sheet, and the opportunity to question the study team, or other independent parties to decide whether they will participate in the study.

Written informed consent will then be obtained by means of participant dated signature and dated signature of the person who presented and obtained the informed consent. The person who obtained the consent will be suitably qualified and experienced, and have been authorised to do so by the Chief/Principal Investigator as detailed on the Delegation of Authority and Signature log for the study. The original signed form will be retained at the study site within the Trial Master File (TMF) or Investigator Site File (ISF). A copy of the signed informed consent will be given to participants (or emailed to participants at their request) and a copy retained in the participant medical notes. Written informed consent will be taken prior to any assessments.

8.2 *Screening and Eligibility Assessment*

Potential participants who are patients on haemodialysis will be screened prior to initial telephone contact by a member of the clinical team involved in patient care based on the

Date: 03/05/2022 Version 4.1

inclusion/exclusion criteria against patients. The clinical team will also screen clinic lists and the COVID-19 vaccination log on PROTON (see above) to identify and approach potential participants at routine dialysis sessions.

Potential participants who are healthy volunteers will be NHS workers at the University Hospital of Leicester. It is anticipated that NHS workers will be amongst the first groups of people to receive the vaccine and these people will be made aware of the study through local poster advertisements in the department of renal medicine at the University Hospitals. Those interested in participating will be asked to contact the study team via email and the study team will then make contact to screen for eligibility, send the PIS and invite to take part as required.

8.3 *Assessments*

For patients on haemodialysis, blood sampling for IgG antibody response to COVID-19 vaccination will take place when the patient attends a routine dialysis appointment 1 month post first vaccination dose and 1 month and 6 months post second vaccination dose (3 samples total). A baseline sample will be obtained from routinely stored clinical samples. Blood will be taken during the patients dialysis at the same time as bloods for routine clinical care with no additional procedures needed when blood is taken. Vaccines currently available or soon to be available require 2 doses before immunity is achieved and the blood antibody tests will be taken 1 month after the first immunisation has been administered and 1 month and 6 months after the second. Blood will be taken from the arterial dialysis line at the start of dialysis so no additional venepuncture is required and no additional visits to a clinical environment are required.

Healthy volunteers will be working in a clinical environment within UHL and will have their blood taken by a trained member of the research team (all of whom are working on the clinical service at UHL) at baseline, 1 month post the first vaccination dose and 1 month and 6 months after the second vaccination dose. This will be arranged in the most practical way and will conform to Hospital protocols on the wearing of personal protective equipment in the clinical environment the blood is taken.

Some of each sample will be processed in the laboratories at the University Hospitals of Leicester, and some will be processed and stored at the University of Leicester. One aliquot

Date: 03/05/2022 Version 4.1

of the stored samples will be transferred in accordance with a Material Transfer Agreement to the Francis Crick Institute (London).

Clinical Information

With the participant's consent, the researcher team will access their clinical records and extract relevant medical and demographic information including:

- Age
- Gender
- Ethnicity
- Primary cause of renal failure
- Previous history of transplantation
- Time on dialysis
- Co-morbidities
- Blood test results
- Medication
- Smoking Habits
- The specific vaccine administered (make/type)

Past medical history, patient demographics, medications and relevant test results will be recorded for healthy volunteers in the same way through access of medical records.

All information will be entered into a case report form (CRFs) which will be stored in a locked filing cabinet in the locked office of the Chief Investigator at the Leicester General Hospital. Data will be extracted from the CRF and entered into an excel spreadsheet that is a coded and anonymised with no patient information which is stored on the UHL CardioRenal Research drive on NHS servers only accessible by members of the research team with specific access.

Laboratory Tests

30 ml (2 tablespoons) of venous blood samples will be taken from the arm by a trained member of the research team/clinical phlebotomy service at 1 month after the first vaccination dose and 1 month and 6 months after the second vaccination dose and using the Monovette System. A baseline sample will also be taken from healthy controls (the patient baseline sample will be extracted from routinely stored clinical samples).

Date: 03/05/2022 Version 4.1

Blood samples from each participant will be sent to the pathology labs for analysis and will be destroyed after the test is completed by the UHL pathology staff.

Additional serum will be separated and stored in aliquots at -80°C at the University of Leicester (Maurice Shock Building, Level 1 Renal Research Laboratory).

One aliquot per time point of the stored samples will be transferred in accordance with the details of a Material Transfer Agreement to the Francis Crick Institute (London) for further antibody analysis. Routinely stored clinical samples for patients (baseline) will also be transferred to the Francis Crick Institute. Any aliquots that have been transferred to the Francis Crick Institute will be disposed of after analysis is completed not stored or transferred back to the University of Leicester.

Aliquots of stored samples will be transferred to additional collaborating sites with ethical approval to conduct analyses that cannot be completed locally in accordance with details of the Material Transfer Agreements drawn up between the University of Leicester and the collaborating centre. Any samples that are transferred externally will be disposed of after analysis is complete, not transferred back to the University of Leicester.

Questionnaires

A short survey pack will be administered at the point of consent containing the following: This will take less than 5 minutes to complete.

Section 1: General Practice Physical Activity Questionnaire (GPPAQ)

Section 2: PROMIS Global Health Scale

Section 3: Pittsburgh Sleep Quality Index (PSQI)

8.4 *Definition of End of Trial*

National Research Ethics Service (NRES)/Health Research Authority (HRA) standard operating procedures advise that the end of the research should be defined in relation to the collection of all data required to answer the research questions in the protocol. In the current study, this will be once all outcome measures have been analysed.

8.5 *Discontinuation/Withdrawal of Participants from Study Treatment*

Date: 03/05/2022 Version 4.1

Each participant has the right to withdraw from the study at any time without giving a reason. In addition, the investigator may discontinue a participant from the study at any time if the investigator considers it necessary for any reason including:

- Significant protocol deviation
- Significant non-compliance with treatment regimen or study requirements
- An adverse event which requires discontinuation of the study or results in inability to continue to comply with study procedures
- Disease progression which requires discontinuation of the study or results in inability to continue to comply with study procedures
- Consent withdrawn
- Lost to follow up

If the participant is withdrawn due to an adverse event, the investigator will arrange for follow-up visits or telephone calls until the adverse event has resolved or stabilised.

8.6 *Source Data*

Source documents are original documents, data, and records from which participants' CRF data are obtained. In this trial, these will include:

- Hospital records (from which medical history and previous and concurrent medication may be summarised into the eCRF)
- Questionnaire pack

In this study the eCRF will be used as the source document to store data extracted from:

- Clinical and demographic data
- Clinical blood results
- IgG Antibody results

All documents will be stored safely in confidential conditions on the UHL Renal Research drive. On all study-specific documents, other than the signed consent, the participant will be referred to by the study participant number/code, not by name.

Date: 03/05/2022 Version 4.1

